### 8.2.1.4. **Assessment of Relationship to Study Drug**

The investigator’s assessment of an AE’s relationship to study drug is part of the documentation process but is not a factor in determining what is or is not reported in the study.

The investigator will assess causality (i.e., whether there is a reasonable possibility that the study drug caused the event) for all AEs and SAEs. The relationship will be classified as follows:

- Not related: There is not a reasonable possibility of relationship to study drug. The AE does not follow a reasonable temporal sequence from study drug administration or can be

reasonably explained by the subject's clinical state or other factors (e.g., disease under study, concurrent diseases, and concomitant medications).

- **Unlikely Related:** when the temporal association between the AE and the drug is such that the drug is not likely to have any reasonable association with the AE
- **Possibly Related:** when the AE follows a reasonable temporal sequence from the time of drug administration **but** it could have been produced by the subject's clinical state or the study procedures/conditions
- **Related:** There is a reasonable possibility of relationship to study drug. The AE follows a reasonable temporal sequence from study drug administration and cannot be reasonably explained by the subject's clinical state or other factors (e.g., disease under study, concurrent diseases, or concomitant medications), represents a known reaction to the study drug or other drugs in its class, is consistent with the known pharmacologic properties of the study drug, and/or resolves with discontinuation of the study drug (and/or recurs with re-challenge, if applicable).

#### **8.2.1.5. Assessment of Expectedness**

An AE or suspected adverse reaction is considered “unexpected” if it is not listed in the Investigator Brochure or package inserts of the individual components of the IMP, or if it occurs with specificity or severity that has not been previously observed with the study drug being tested; or, if an investigator brochure is not required or available, the AE or suspected adverse reaction is not consistent with the risk information described in the general investigational plan or elsewhere in the current application. For example, under this definition, hepatic necrosis would be unexpected (by virtue of greater severity) if the investigator brochure referred only to elevated hepatic enzymes or hepatitis. Similarly, cerebral thromboembolism and cerebral vasculitis would be unexpected (by virtue of greater specificity) if the investigator brochure listed only cerebral vascular accidents. “Unexpected,” as used in this definition, also refers to AEs or suspected adverse reactions that are mentioned in the investigator brochure as occurring with a class of drugs or as anticipated from the pharmacologic properties of the drug but are not specifically mentioned as occurring with the particular drug under investigation.

#### **8.2.1.6. Adverse Event Reporting and Follow-up Period**

The AE reporting period begins at the time of first dose of study drug and ends 30 days after the last dose of study drug.

During the treatment period of the study, participants will be asked about AEs. All AEs that occur during the course of the study must be collected, documented, and reported to the principal investigator. The occurrence of AEs will be assessed at baseline and daily while in the clinical research unit and at each follow-up clinic visit.

Subjects will be asked a standard question to elicit any medically related changes in their well-being. They will also be asked if they have used any new medications or changed concomitant medication regimens (both prescription and over-the-counter medications).

In addition to subject observations, AEs will be documented from any data collected on the AE page of the eCRF (eg, laboratory values, physical examination findings, and ECG changes) or other documents that are relevant to subject safety.

All AEs and SAEs observed while a subject is receiving study drug should be followed until they are resolved, stable, or judged by the investigator to be not clinically significant.

#### **8.2.1.7. Recording of Adverse Events**

All AEs reported or observed during the study will be recorded on the AE page of the eCRF. Information to be collected includes dose level, type and frequency of event, date and time of onset, investigator-specified assessment of severity and relationship to study drug, date, and time of resolution of the event, seriousness, any required treatment or evaluations, and outcome. Any AEs resulting from concurrent illnesses, reactions to concurrent illnesses, reactions to concurrent medications, or progression of disease states must also be reported. All AEs will be followed until they are resolved, stable, or judged by the investigator to be not clinically significant. MedDRA (version 23.0 or higher) will be used to code all AEs.

#### **8.2.1.8. Serious Adverse Event Reporting**

Any AE that is considered serious by the investigator or which meets SAE criteria (Section 8.1.1.2) must be reported to the sponsor immediately (after the investigator has confirmed the occurrence of the SAE). The investigator and the study medical monitors will assess whether there is a reasonable possibility that the study drug caused the SAE. The sponsor will be responsible for notifying the relevant regulatory authorities of any SAE as outlined in US Title 21 Code of Federal Regulations (CFR) Parts 312 and 320. The investigator is responsible for notifying the IRB directly.

For this study, the following contact information is to be used for SAE reporting:

Lotus Medical Monitor:

[REDACTED]

24/7 SAE and medical question hotline: [REDACTED]

SAE email:

[REDACTED]

Sponsor Medical Monitor:

[REDACTED]

Xgene Pharmaceutical Inc.

Email: [REDACTED]

Telephone: [REDACTED]

### 8.2.1.9. Reporting of Pregnancy

Pregnancy diagnosed during the study, or that occurs within 30 days after stopping study medication, must be reported immediately to the Investigator. Pregnancy, in and of itself, is not regarded as an adverse event, unless there is suspicion that study medication may have interfered with the effectiveness of a contraceptive medication. If the subject becomes pregnant while on-study, the study drug must be immediately discontinued. Pregnancy information about a female subject or a female partner of a male subject should be reported immediately from the time the Investigator first becomes aware of a pregnancy or its outcome. This will be performed by the Investigator completing a Pregnancy Form.

Any pregnancy complication, spontaneous abortion, elective termination of a pregnancy for medical reasons, outcome of stillbirth, congenital anomaly/birth defect, or serious adverse event in the mother will be recorded as an SAE and will be reported as described in Section 8.2.1.8.

### 8.2.2. Clinical Laboratory Assessments

Clinical laboratory samples will be analyzed at the central laboratory.

Blood and urinalysis samples will be collected. The following standard clinical laboratory assessments will be performed at the time points indicated in the SOA ([Section 1.2](#)).

Hematology: Complete blood count including hemoglobin, hematocrit, RBC count, RBC indices, MCH, MCHC, platelet count, and WBC count including differential. HbA1c will be assessed at Screening only.

Coagulation: PT, PTT, and fibrinogen

Serum Chemistry: Albumin, total bilirubin, total protein, calcium, ALP, ALT, AST, BUN, creatinine, glucose, sodium, potassium, chloride, bicarbonate, LDH, and uric acid. Creatinine clearance will be calculated by the Cockcroft/Gault formula ([Cockcroft DW, Gault MH. Prediction of creatinine clearance from serum creatinine. Nephron 1976;16: 31-41.](#))

Urinalysis: pH, specific gravity, blood and leukocyte esterase, glucose, protein, and ketones

Serology: Hepatitis B virus surface antigen, hepatitis B anti-core antibody (anti-HBc) and anti-surface antibody, hepatitis C virus antibody, and HIV antibody types 1 and 2 (Screening only)

All subjects will undergo a urine drug screen (amphetamines, barbiturates, benzodiazepines, cocaine, opiates [including heroin, codeine, and oxycodone], phencyclidine [PCP], THC, methamphetamines, methadone, and ecstasy), and alcohol screen at Screening only.

A serum pregnancy test will be performed at Screening and a urine pregnancy test on Day 1 prior to dosing only in premenopausal women of childbearing potential or women who are not surgically sterile. Results must be available before surgery.

Clinical laboratory tests may be repeated at the discretion of the investigator, if necessary, for assessment of inclusion and exclusion criteria or evaluation of clinical laboratory abnormalities.

### **8.3. Pharmacokinetic Assessments**

#### **8.3.1. Pharmacokinetic Sampling and Analysis**

Blood draws will always be performed after each NPRS, nausea, SIS and/or PGA assessment, when applicable, and prior to the first administration of rescue medication. The PK sampling plan uses the post-end-of-surgery schedule to be consistent with the efficacy assessment schedule.

Each subject in the PK subgroup (one site only) will have blood samples drawn for PK assessments at the following time points: prior to the first dose (pre-dose), and post end of surgery at 1, 2, 3, 4, 6, 8, 10, 12, 24, 30, 36, 42, 48, 54, 60, 66, and 72 hours within a  $\pm 15$ -minute window. The actual clock time when the PK sample is collected will be recorded, and the post-dose time for PK analysis will be calculated based on the recorded clock time.

The timing and frequency of PK sample collection is listed in the SOA ([Section 1.2](#)).

Details for the collection, processing, storage, and shipping of PK samples will be provided to the clinical unit separately.

Pharmacokinetic samples will be analyzed using a validated liquid chromatography coupled with tandem mass spectrometry assay for XG005 in human plasma. Assay details, results, and validation will be provided in a separate bioanalytical report.

## 9. STATISTICAL METHODS AND DATA ANALYSIS

Full details of the statistical analysis methodology will be provided in a separate Statistical Analysis Plan (SAP). A separate PK analysis plan will also be prepared.

A change to the data analysis methods described in the protocol will require a protocol amendment only if it alters a principal feature of the protocol. The SAP will be finalized prior to database lock. Any changes to the methods described in the final SAP will be described and justified in the clinical study report.

### 9.1. Statistical Hypotheses

This primary efficacy endpoint is to test the mean difference of summed pain intensity from end of surgery to 48 hours post-surgery (SPI48) between high dose XG005 and Placebo groups.

The study null hypothesis is XG005 high dose and placebo have the same effect. And the alternative hypothesis is XG005 high dose and placebo have different effect. These will be tested at a two-tailed alpha of 0.05, and the Null hypothesis will be rejected if p-value < 0.05.

### 9.2. Sample Size Determination

One hundred thirty (130) evaluable subjects per study arm will yield 90% power to detect a standardized effect size of 40% (Wang 2010; Wu J, Jiang J, Wei W. Confidence intervals of effect size in randomized comparative parallel-group studies. *Stat Med*. 2006;25(4):639-51.; Vevea J, Woods CM. Publication bias in research synthesis: sensitivity analysis using A priori weight functions. *Psychological Methods*. 2005;10(4):428-43.; Singla NK, Chelly JE, Lionberger DR, et al. Pregabalin for the treatment of postoperative pain: results from three controlled trials using different surgical models. *J Pain Res*. 2015;8:9-20.) at a two-tailed  $\alpha = 0.05$  for the familywise type one error. Recruitment goals will be 150 subjects per arm or N=450 total.

Randomization Strata: Study Site

### 9.3. Multiplicity Adjustment

A serial gatekeeping procedure will be used to control the overall type-1 error rate at 0.05 for primary and secondary endpoints. If the primary endpoint is not significant at a two-tailed alpha of 0.05, there is no testing on secondary endpoints. If the primary endpoint is significant at a two-tailed alpha of 0.05, the secondary endpoints will be tested following the hierarchy testing procedure with a pre-specified order as Section 3. If any secondary endpoint is not significant, the successive secondary endpoints will not be tested.

### 9.4. Populations

- The Intent-to-Treat (ITT) population is defined as all randomized subjects. Subjects will be analyzed according to the treatment group to which they were randomized.
- The Safety Population is defined as all subjects who receive study medication. Subjects will be analyzed according to the actual treatment they receive.

- The modified Intent-to-Treat (mITT) Population is defined as all ITT subjects who received at least one dose of study medication and have at least 2 NPRS assessments post-end of surgery.
- The Per-Protocol Population is defined as all mITT subjects who have no major protocol violations which may potentially bias efficacy analysis of the study.

## **9.5. Statistical Analyses**

### **9.5.1. General Approach**

All data collected will be presented in data listings. Data from subjects excluded from an analysis population will be presented in the data listings, but not included in the calculation of summary statistics.

For categorical variables, frequencies and percentages will be presented. Continuous variables will be summarized using descriptive statistics (number of subjects, mean, median, standard deviation (SD), minimum and maximum).

Baseline demographic and background variables will be summarized overall for all subjects. The number of subjects who enroll in the study and the number and percentage of subjects who complete the study will be presented. Frequency and percentage of subjects who withdraw or discontinue from the study, and the reason for withdrawal or discontinuation, will also be summarized.

### **9.5.2. Efficacy Analyses**

The primary endpoint of the comparison of summed pain intensity (SPI) from end of surgery to 48 hours post-surgery (SPI48) for high dose XG005 vs placebo will be analyzed, using analysis of covariance (ANCOVA) model. The model will use treatment as main effect, and study site as a covariate. More details for efficacy analyses will be specified in SAP.

### **9.5.3. Safety Analyses**

Adverse events will be coded by preferred term and system organ class (SOC) using the latest version of MedDRA (version 23 or higher). All AE data will be presented in a data listing. Treatment-emergent AEs will be summarized by treatment and overall, as well as by severity and relationship to study drug. Serious AEs and AEs leading to discontinuation of study drug will also be presented in the data listings and summarized by treatment and overall.

Actual values and changes from baseline for clinical laboratory test results, vital sign measurements, and 12-lead ECG results will be summarized by treatment at each time point using descriptive statistics (number of subjects, mean, SD, median, minimum, and maximum). Shift tables will be generated for clinical laboratory test results. Physical examination findings will be presented in a data listing.

#### **9.5.4. Pharmacokinetic Analyses**

PK analyses will be addressed in a separate PK Analysis Plan.

Individual plasma concentrations of naproxen, pregabalin and XG005 (and/or other metabolites as appropriate) will be listed by subject and summarized by gender, dose, and nominal time point using descriptive statistics (i.e., N, arithmetic mean, SD, percent coefficient of variation [CV%], median, minimum, maximum, and geometric mean).

The PK parameters of XG005 will be analyzed based on the actual sampling times. All parameters will be calculated using the latest version of Phoenix® WinNonlin® (Certara USA Inc., Princeton, New Jersey) or SAS® (SAS Institute Inc., Cary, North Carolina). Pharmacokinetic parameters will be summarized by time point for each dose level using descriptive statistics (number of subjects, mean, SD, CV, median, minimum, and maximum). Geometric means will be reported for  $AUC_{0-t}$ ,  $AUC_{0-inf}$ ,  $AUC_{0-48}$ , and  $C_{max}$ .

#### **9.5.5. Handling of Missing Data**

For the PK analysis, concentrations that are below the limit of quantification (BLQ) will be treated as zero for descriptive statistics with the exception that a BLQ value between two quantifiable concentrations will be set as missing. Missing concentrations will be treated as missing from the PK parameter calculations. If consecutive BLQ concentrations are followed by quantifiable concentrations in the terminal phase, those concentrations after BLQ concentrations will be treated as missing.

For efficacy analyses, when rescue medication is used, the last pain intensity measure prior to the use of rescue medication will be used (imputed) for the subsequent protocol-specified time points for measurement of pain intensity after the time of the rescue medication.

Missing data as a result of discontinuation due to adverse event or due to lack of efficacy will be imputed with worst observation carry forward (WOCF) method.

For safety analyses, missing data will not be imputed in general, otherwise specified.

More detail will be described in the SAP.

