
 
To investigate the PK of XG005, naproxen, and pregabalin in a perioperative population
 
	
 
Area under the plasma concentration-time curve from time zero to time <math>t</math> of the last measured concentration above the limit of quantification (AUC0-last)
 
Area under the plasma concentration-time curve from zero to infinity (AUC0-inf)
 
Maximum plasma concentration (Cmax)
 
Trough plasma concentration prior to each dose (Ctrough)
 
Time to reach maximum plasma concentration (Tmax)
 
Terminal elimination rate constant (<math>\lambda_z</math>) with the respective half-life (t1/2).
 

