### 6.2. Dosing and Administration

Study drug (XG005 low or high dose, or placebo) will be administered as an oral dose 60 minutes prior to surgery on Day 1 then every 12 hours for 72 hours after the time of first dose. The number and strength of active drug tablets to be administered at each dose level is shown in Table 1. Subjects randomized to placebo will receive the corresponding number of placebo tablets.

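### The BLQ-to-missing rule in Section 9.5.5 has no limit for 12-hourly dosing, so it can delete genuine late-interval XG005 values and bias their summaries upward

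*Combined protocol and SAP*

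**What the plan says.** Section 9.5.5, repeated in the synopsis under Statistical Considerations, sets four rules for PK data:

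- By default, "concentrations that are below the limit of quantification (BLQ) will be treated as zero for descriptive statistics".
- The exception is that "a BLQ value between two quantifiable concentrations will be set as missing".
- The deletion carries forward: "Missing concentrations will be treated as missing from the PK parameter calculations".
- A separate sentence covers runs. "If consecutive BLQ concentrations are followed by quantifiable concentrations in the terminal phase", the later values are dropped. The terminal phase is not defined for repeated doses.

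Under Section 6.2, study drug is given "60 minutes prior to surgery on Day 1 then every 12 hours for 72 hours after the time of first dose". Under Section 8.3.1, PK samples are taken pre-dose and then at "1, 2, 3, 4, 6, 8, 10, 12, 24, 30, 36, 42, 48, 54, 60, 66, and 72 hours" after end of surgery. XG005, naproxen and pregabalin are all assayed (Schedule of Assessments, footnote l). Section 9.5.4 summarises each analyte by nominal time point, with arithmetic and geometric means. Section 3 lists AUC to the last quantifiable time and "Trough plasma concentration prior to each dose" among the PK endpoints. Section 9.5.4 refers PK analysis to a separate PK Analysis Plan, which is not among the documents.

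**The concern.** After a single dose, a BLQ result between two quantifiable ones is suspect, since a falling curve should not dip below the limit and come back. Setting it to missing is then reasonable. Under repeat dosing the same pattern can be real: concentration falls late in one interval and rises again after the next dose. The rule as worded cannot tell the two situations apart.

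The analyte at issue is XG005 itself, which Section 4.2 describes as hydrolysed to naproxen and pregabalin. If it clears within the interval, the lowest values would be removed selectively. Descriptive means at late-interval times would then rest only on subjects who still had measurable prodrug.

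**Working it through.** **There is no planned figure to reproduce.** The documents state no BLQ frequency, quantification limit (LLOQ) or XG005 half-life. Two checks were made.

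**1. Where the samples fall in the dosing interval**

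Inputs: surgery starts 60 ± 10 minutes after dose 1 (synopsis), so 50 to 70 minutes. Surgery lasts at most 90 minutes (Section 6.5.5). No minimum is stated, so 30 minutes is assumed. Doses are taken at 0, 12, ..., 72 h.

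End of surgery after dose 1: (50 + 30)/60 = 1.3 h to (70 + 90)/60 = 2.7 h.

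| Sample (h after surgery) | Hours since last dose |
|---|---|
| 8 | 9.3 to 10.7 |
| 10 | 11.3 to 12.7 after dose 1, so at or around dose 2 |
| 12, 24, 36, 48, 60, 72 | 1.3 to 2.7 |
| 30, 42, 54, 66 | 7.3 to 8.7 |

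From 24 h on, samples alternate between early and late in an interval. A BLQ value at 30, 42, 54 or 66 h has an early sample from its own interval before it and an early sample from the next interval after it. The 10 h sample, when it falls before dose 2, has the 8 h sample before it and a post-dose-2 sample after it.

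The 66 h entry assumes a dose at 72 h. If the last dose is at 60 h, the 66 and 72 h samples share an interval and 66 h drops off the list.

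**2. What deletion does to the mean**

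Concentration at one time point is taken as lognormal with σ² = ln(1 + CV²). A fraction p lies below the LLOQ, and z is the standard normal p-quantile. Relative to the true mean m:

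- BLQ deleted: Φ(σ − z)/(1 − p) − 1
- BLQ set to zero: Φ(σ − z) − 1
- BLQ set to LLOQ/2: Φ(σ − z) + 0.5·p·LLOQ/m − 1

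Example, CV 100% and p = 0.30: σ = √ln 2 = 0.833 and z = −0.524, so Φ(1.357) = 0.913. Deletion gives 0.913/0.70 − 1 = +30%. Zero gives −9%.

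| Assumed p | Deleted (CV 50% / 100%) | Zero | LLOQ/2 | Subjects left of 30 |
|---|---|---|---|---|
| 10% | +7% / +9% | −4% / −2% | −2% / −1% | 27 |
| 30% | +20% / +30% | −16% / −9% | −5% / −2% | 21 |
| 50% | +36% / +59% | −32% / −20% | −9% / −3% | 15 |

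A simulation of 50,000 groups of 30 at CV 100% and p = 30%, in LLOQ units, gave a true mean of 2.19, a mean of 2.85 with deletion and 2.00 with zero. This agrees with the formulas (2.19, 2.85, 2.00).

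**AUC illustration.** Assume linear trapezoids and the same value C at 24 and 36 h. With the 30 h value deleted, the area is 12 × (C + C)/2 = 12C. With it kept as zero, the area is 6 × C/2 + 6 × C/2 = 6C. The contribution of that interval doubles. The plan's zero rule is worded for descriptive statistics only, so how a retained BLQ value enters AUC also needs stating.

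**The case against.** The strongest reply is that this may never matter. Nothing in the documents shows that XG005 falls below the limit within 12 hours, and hydrolysis alone gives no rate. PK is descriptive, in about 60 active-arm subjects at one site. Section 4.2 attributes the analgesic effect wholly to naproxen and pregabalin. Naproxen's half-life of 12 to 17 hours (Section 4.3) makes a BLQ value within an interval implausible, and nothing is shown for pregabalin. The PK Analysis Plan might also narrow the rule. All of this stands as a limit on size. Deferral does not remove the point, because the protocol already states the rule, and the later plan must follow it or contradict it.

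A reader might infer more than the text supports:

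- **That Ctrough is biased at every dose.** Only the 10 h sample is near a pre-dose time. No scheduled sample falls just before the later doses, so there is little scheduled trough data for the rule to distort.
- **That nearly all true BLQ results are discarded.** The exception is worded for a single value. A run, for example at 6, 8 and 10 h, is not plainly caught by it.
- **That accumulation is overstated.** Accumulation is not a listed endpoint. Cmax and Tmax do not change when a BLQ value is dropped.
- **That the inflation is 1/(1 − p), or 1.11, 1.43 and 2.0 at 10%, 30% and 50% BLQ.** That ratio compares deletion with BLQ set to zero, which is itself too low. Against the true mean the excess is smaller, as tabulated.

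It is also fair to object that returning to zero is not clean. It biases the arithmetic mean downward, and it leaves the planned geometric mean zero or undefined.

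**Conclusion.** The point holds as a conditional, minor defect in the rule. The wording has no repeat-dose limit, and the schedule makes a single late-interval BLQ value look embedded. If the neighbours are quantifiable, deletion biases upward the XG005 mean at 10, 30, 42, 54 and 66 h, AUClast, and the one near-trough sample at 10 h.

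Whether this happens, and how often, cannot be told from the documents. The percentages rest on assumed BLQ fractions and lognormal CVs, and the sample timing rests on an assumed 30-minute minimum surgery. The direction for any value so deleted needs neither assumption. The consequence is confined to XG005 descriptive PK.

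**What to change.** In Section 9.5.5, the synopsis and the PK Analysis Plan:

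1. Set an embedded BLQ value to missing only when both flanking quantifiable values lie in the same dosing interval, judged by actual dose and sample times.
2. Keep a BLQ value that precedes the next dose in the descriptive statistics and parameter calculations under a stated substitution. Use the plan's zero rule for the arithmetic mean. Use LLOQ/2 or a censored-data method for the geometric mean and as a sensitivity check. Name the substitution used for AUC.
3. Report the number of BLQ values at each nominal time point, by arm and analyte.
4. Apply the consecutive-BLQ rule only after the final dose, and define the terminal phase that way.

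The cost is a few sentences and a little more PK programming, with no new samples. No substitution is free of bias: at 30% BLQ, zero gives about −9% to −16% under the same assumptions. That is smaller than the +20% to +30% from deletion, and the BLQ counts let the reader judge it.
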